The primary endpoint was survival without mechanical ventilation (SWOV) through day 28, using a time to event approach. The Kaplan-Meier (KM) estimate of failure to achieve SWOV by Day 28 was 15.6% (11.5-20.9) in the lenzilumab group compared to 22.1% (17.4-27.9) in the placebo group (Hazard Ratio [HR] = 1.54, $p=0.0403$, mITT; [Figure 2A](#)).⁽⁶⁾ In a post hoc analysis, the subgroup of subjects with a CRP < 150 mg/L and age < 85 years, the KM estimate of failure to achieve SWOV was 8.5% (5.0-14.1) in the lenzilumab group compared to 21.2% (15.9-28.1) in the placebo group (HR=2.96, $p=0.0003$, mITT; [Figure 2B](#)). A similar treatment effect was observed when evaluating those that received remdesivir (15.6% vs 25.7%, HR=1.91, $p=0.0073$, mITT) as well as remdesivir + steroids (16.3% vs 26.9%, HR=1.92, $p=0.0067$, mITT). Mortality in the full population did not reach a statistically significant difference (9.5 in lenzilumab arm vs 13.9% in placebo, HR=1.38, $p=0.241$), but in the subgroup of subjects with a CRP < 150 mg/L and age < 85 years this was statistically significant (6.5% vs 13.8%, HR=2.2, $p=0.033$, no adjustments for multiple comparisons).

Figure 3. Kaplan-Meier plot of Survival Without Ventilation. A. Plot for mITT population. B. Plot for mITT population with baseline CRP<150 mg/L .

Based on the results from the LIVE-AIR trial (and with no knowledge of unblinded interim results from this trial), consideration was made to expanding BET-B from a phase 2 to a phase 2/3 to serve as a confirmatory pivotal trial. This could be accomplished with a larger sample size. These changes were implemented in v5 of the protocol.

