c Sensitivity Analysis 2: Odds Ratios of Active treatment vs Placebo calculated from the logistic regression model adjusted for baseline dexamethasone use, baseline OS, age (continuous), and baseline CRP. Subjects without event whose last assessment is in window for Day 29 (Day 26, 27, 28) are considered missing. Missing data imputed using the 3-stage imputation procedure described in Section 6.5.												
d Sensitivity Analysis 3: Same imputation as initial model in a . The final model also includes categorical age and geographical regions as covariates.												
e Sensitivity Analysis 4: PROC MI part of the imputation model uses FCS logistic instead of monotone logistic. The rest of the imputation procedure and final covariates are similar to those in the initial model in a .												
f TMLE Approach 1: Estimates marginal ORs and risk differences using TMLE and adjusts for all missing data using the missing indicator functionality of TMLE.												
g TMLE Approach 2: Estimates marginal ORs and risk differences using MI combining TMLE analysis in imputed datasets. Missing events for discharged subjects are considered non-events, missing events for subjects with no post baseline data are handled using the missing indicator in TMLE, while a similar MI procedure as the primary analysis is used to impute missing event for subjects who were hospitalized or transferred to another hospital at their last assessment.												
h For the subgroup analyses, the model described in a was performed for each level of the subgroup without multiple imputation. P-value from the interaction between the subgroup variable and treatment group is also reported.												
i Estimate and 95% CI for the proportion are estimated using either logistic regression or TMLE.												
j Risk Differences calculated using the approach described in Ge.et al [1] or TMLE. CIs calculated using bootstrap or TMLE.												
k P-value from the logistic regression model or TMLE. For the interaction, P-value from interaction Type III test in subgroup analysis where the interaction between subgroup and treatment is being added to the logistic regression model.												

Tables with similar format:

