**Table 5: Proportion of Subjects Alive and Without Mechanical Ventilation through Day 29 — ITT Population**

*[Implementation note: Add subgroup analysis for baseline CRP < 150 mg/L vs baseline CRP ≥ 150 mg/L. Add footnote that analysis for this subgroup analysis will only include subjects in the ITT population with baseline ordinal score of 5 or 6 and age<85years.]*

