**Table 11: Time to Sustained Recovery through Day 60 — ITT Population**

*[Implementation note: Add subgroup analysis for baseline CRP < 150 mg/L vs baseline CRP  $\geq$  150 mg/L. Add footnote that analysis for this subgroup analysis will only include subjects in the ITT population with baseline ordinal score of 5 or 6 and age < 85 years.]*

**Table 12: Time to Sustained Recovery through Day 60 by Treatment Group, Actual Baseline Ordinal Score, and Analysis Population: Restricted Mean Survival Time Analysis**

Analysis Population	Treatment Group	Actual Baseline Ordinal Score	n	Tau a	Restricted Mean Recovery Time (Days)		Difference	
					Estimate	95% CI	Estimate	95% CI
ITT with BOS 5 or 6, CRP<150 mg/L, and age<85 years	Lenzilumab + RDV (N=X)	5	x	x	x.x	x.x, x.x	x.xx	x.xx, x.xx
	Placebo + RDV (N=X)		x	x	x.x	x.x, x.x		
	Lenzilumab + RDV (N=X)	6	x	x	x.x	x.x, x.x	x.xx	x.xx, x.xx
	Placebo + RDV (N=X)		x	x	x.x	x.x, x.x		
	Lenzilumab + RDV (N=X)	Any BOS b	x	x	x.x	x.x, x.x	x.xx	x.xx, x.xx
	Placebo + RDV (N=X)		x	x	x.x	x.x, x.x		
ITT	Lenzilumab + RDV (N=X)	5	x	x	x.x	x.x, x.x	x.xx	x.xx, x.xx
	Placebo + RDV (N=X)		x	x	x.x	x.x, x.x		
	Lenzilumab + RDV (N=X)	6	x	x	x.x	x.x, x.x	x.xx	x.xx, x.xx
	Placebo + RDV (N=X)		x	x	x.x	x.x, x.x		
	Lenzilumab + RDV (N=X)	7	x	x	x.x	x.x, x.x	x.xx	x.xx, x.xx
	Placebo + RDV (N=X)		x	x	x.x	x.x, x.x		
	Lenzilumab + RDV (N=X)	Any BOS b	x	x	x.x	x.x, x.x	x.xx	x.xx, x.xx
	Placebo + RDV (N=X)		x	x	x.x	x.x, x.x		

N= Number of subjects in the specified treatment group, actual baseline ordinal score, and analysis population.

n = Number of recovered subjects.

Difference is the difference in the restricted mean recovery time between active treatment to placebo.

a Tau is the truncation time point for the Restricted Mean Survival Time analysis and is equal to the minimum of the largest observed times in each group.

b There were X additional subjects with an Actual Baseline Ordinal Score of 4 that are included in the 'Any BOS' summaries.

Programming notes:

Within an actual baseline ordinal score stratum:

```
proc lifetest data=enrevent plots=(rmst) method=breslow rmst(cl);
by stratum;
time evntday * Censor(1);
strata trtcode /diff=all;
ods output rmst=rmst;
run;
```

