**Table 13: Mortality Rates — ITT Population with Baseline Ordinal Score of 5 or 6, CRP<150 mg/L, and age<85 years**

Analysis Type	Baseline Ordinal Score	Treatment Group	Number of Deaths		Mortality Rate (CI) c			Difference in Mortality Rates at the Specified Time Point d			HR e			P-value f
			n	%	Estimate	80% CI	95% CI	Estimate	80% CI	95% CI	Estimate	80% CI	95% CI	
Time to Death by Day 15														
Primary a	5	Lenzilumab + RDV (N=X)	X	x.x	x.x	x.x, x.x	x.fff	x.x	x.x, x.x	x.x, x.x	x.x	x.x, x.x	x.x, x.x	0.fff
		Placebo + RDV (N=X)	X	x.x	x.xx	x.x, x.x	x.fff							
	6	Lenzilumab + RDV (N=X)	X	x.x	x.x	x.x, x.x	x.fff	x.x	x.x, x.x	x.x, x.x	x.x	x.x, x.x	x.x, x.x	0.fff
		Placebo + RDV (N=X)	X	x.x	x.xx	x.x, x.x	x.fff							
	7	Lenzilumab + RDV (N=X)	X	x.x	x.x	x.x, x.x	x.fff	x.x	x.x, x.x	x.x, x.x	x.x	x.x, x.x	x.x, x.x	0.fff
		Placebo + RDV (N=X)	X	x.x	x.xx	x.x, x.x	x.fff							
	Any BOS	Lenzilumab + RDV (N=X)	X	x.x	x.x	x.x, x.x	x.fff	x.x	x.x, x.x	x.x, x.x	x.x	x.x, x.x	x.x, x.x	0.fff
		Placebo + RDV (N=X)	X	x.x	x.xx	x.x, x.x	x.fff							
Primary with Sensitivity Imputation b	5	Lenzilumab + RDV (N=X)	X	x.x	x.x	x.x, x.x	x.fff	x.x	x.x, x.x	x.x, x.x	x.x	x.x, x.x	x.x, x.x	0.fff
		Placebo + RDV (N=X)	X	x.x	x.xx	x.x, x.x	x.fff							
	6	Lenzilumab + RDV (N=X)	X	x.x	x.x	x.x, x.x	x.fff	x.x	x.x, x.x	x.x, x.x	x.x	x.x, x.x	x.x, x.x	0.fff
		Placebo + RDV (N=X)	X	x.x	x.xx	x.x, x.x	x.fff							
	7	Lenzilumab + RDV (N=X)	X	x.x	x.x	x.x, x.x	x.fff	x.x	x.x, x.x	x.x, x.x	x.x	x.x, x.x	x.x, x.x	0.fff
		Placebo + RDV (N=X)	X	x.x	x.xx	x.x, x.x	x.fff							

Analysis Type	Baseline Ordinal Score	Treatment Group	Number of Deaths		Mortality Rate (CI) c			Difference in Mortality Rates at the Specified Time Point d			HR e			P-value f
			n	%	Estimate	80% CI	95% CI	Estimate	80% CI	95% CI	Estimate	80% CI	95% CI	
	Any BOS	Lenzilumab + RDV (N=X)	X	x.x	x.x	x.x, x.x	x.xxx	x.x	x.x, x.x	x.x, x.x	x.x	x.x, x.x	x.x, x.x	0.xxx
		Placebo + RDV (N=X)	X	x.x	x.xx	x.x, x.x	x.xxx							
Time to Death by Day 29														
Primary a	5	Lenzilumab + RDV (N=X)	X	x.x	x.xx	x.x, x.x	x.xxx	x.x	x.x, x.x	x.x, x.x	x.x	x.x, x.x	x.x, x.x	0.xxx
		Placebo + RDV (N=X)	X	x.x	x.xx	x.x, x.x	x.xxx							
	6	Lenzilumab + RDV (N=X)	X	x.x	x.x	x.x, x.x	x.xxx	x.x	x.x, x.x	x.x, x.x	x.x	x.x, x.x	x.x, x.x	0.xxx
		Placebo + RDV (N=X)	X	x.x	x.xx	x.x, x.x	x.xxx							

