Analysis Type	Baseline Ordinal Score	Treatment Group	Number of Deaths		Mortality Rate (CI) c			Difference in Mortality Rates at the Specified Time Point d			HR e			P-value f
			n	%	Estimate	80% CI	95% CI	Estimate	80% CI	95% CI	Estimate	80% CI	95% CI	
7	Lenzilumab + RDV (N=X)	X	x.x	x.x	x.x, x.x	x.XXX	x.x	x.x, x.x	x.x, x.x	x.x	x.x, x.x	x.x, x.x	0.xxx	
		X	x.x	x.xx	x.x, x.x	x.XXX								
	Any BOS	Lenzilumab + RDV (N=X)	X	x.x	x.x	x.x, x.x	x.XXX	x.x	x.x, x.x	x.x	x.x, x.x	x.x, x.x	0.xxx	
		X	x.x	x.xx	x.x, x.x	x.XXX								

CI= Confidence Intervals. N=Number of subjects in the Safety population. n= Number of unique subjects that satisfies the row criteria.

a For the primary endpoint, all subjects whose last assessment was before the corresponding timepoint (Day 15 Visit, Day 29 Visit, Day 60 Visit) and were missing the event were censored at the date of last assessment.

b Primary with Sensitivity Imputation: Same analysis as the initial model but subjects missing event and whose last assessment is before the corresponding timepoint (Day 15 Visit, Day 29 Visit, Day 60 Visit) are non-events for good discharges and censored at Day 15, Day 29, Day 60 respectively or at last assessment for subjects still hospitalized or discharged to LTAC, hospice care, or other hospital.

c Mortality Rates are the Kaplan-Meier estimates.

d Difference in mortality rates (80%, 95% CI) obtained from Kaplan Meier.

e HR is the hazard ratio from the Cox Proportional Hazard Model adjusted for baseline ordinal score and baseline steroid use.

f P-value is based on the Cox adjusted model.

Tables with similar format:

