**Table 14: Mortality Rates — ITT Population**

**Table 15: Mortality Rates — ITT Population with Baseline Ordinal Score of 5 or 6, CRP≥150 mg/L, and age<85 years**

**Table 16: Time to Death by Treatment Group, Actual Baseline Ordinal Score, and Analysis Population: Restricted Mean Survival Time Analysis**

Analysis Population	Treatment Group	Actual Baseline Ordinal Score	n	Tau a	Restricted Mean Time to Death (Days)		Difference				
					Estimate	95% CI	Estimate	95% CI			
Time to Death through Day 15											
ITT with BOS 5 or 6, CRP<150 mg/L, and age<85 years	Lenzilumab + RDV (N=X)	5	x	x	x.x	x.x, x.x	x.xx	x.xx, x.xx			
	Placebo + RDV (N=X)		x	x	x.x	x.x, x.x					
	Lenzilumab + RDV (N=X)	6	x	x	x.x	x.x, x.x	x.xx	x.xx, x.xx			
	Placebo + RDV (N=X)		x	x	x.x	x.x, x.x					
	Lenzilumab + RDV (N=X)	Any BOS b	x	x	x.x	x.x, x.x	x.xx	x.xx, x.xx			
	Placebo + RDV (N=X)		x	x	x.x	x.x, x.x					
ITT	Lenzilumab + RDV (N=X)	5	x	x	x.x	x.x, x.x	x.xx	x.xx, x.xx			
	Placebo + RDV (N=X)		x	x	x.x	x.x, x.x					
	Lenzilumab + RDV (N=X)	6	x	x	x.x	x.x, x.x	x.xx	x.xx, x.xx			
	Placebo + RDV (N=X)		x	x	x.x	x.x, x.x					
	Lenzilumab + RDV (N=X)	7	x	x	x.x	x.x, x.x	x.xx	x.xx, x.xx			
	Placebo + RDV (N=X)		x	x	x.x	x.x, x.x					
	Lenzilumab + RDV (N=X)	Any BOS b	x	x	x.x	x.x, x.x	x.xx	x.xx, x.xx			
	Placebo + RDV (N=X)		x	x	x.x	x.x, x.x					
Time to Death through Day 29											
Time to Death through Day 60											
N= Number of subjects in the specified treatment group, actual baseline ordinal score, and analysis population. n = Number of subjects who died. Difference is the difference in the restricted mean time to death between active treatment to placebo. a Tau is the truncation time point for the Restricted Mean Survival Time analysis and is equal to the minimum of the largest observed times in each group. b There were X additional subjects with an Actual Baseline Ordinal Score of 4 that are included in the 'Any BOS' summaries.											

**Table 17: Summary Results of Tipping Point Analysis for the Proportion of Subjects Alive and Without Mechanical Ventilation through Day 29 — ITT Population with Baseline Ordinal Score of 5 or 6, CRP<150 mg/L, and age<85 years**

Probability of event among nonresponders in Placebo + RDV	Probability of event among nonresponders in Lenzilumab + RDV					
	1%	5%	10%	15%	20%	40%

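### The BET-B SAP tests mortality below and above CRP 150 in separate tables with no row comparing the two effects, so an equal effect can often look confined to CRP<150

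*SAP*

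**What the plan says.** SAP Section 8.3 adds mortality tables for the primary subgroup (Table 13), the full ITT population (Table 14) and subjects with scores 5 or 6, age under 85 and CRP of at least 150 mg/L (Table 15). Table 13 is titled "Mortality Rates — ITT Population with Baseline Ordinal Score of 5 or 6, CRP<150 mg/L, and age<85 years" and Table 15 "Mortality Rates — ITT Population with Baseline Ordinal Score of 5 or 6, CRP≥150 mg/L, and age<85 years"; Tables 14 and 15 follow the Table 13 format.

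That format gives Kaplan-Meier mortality, the difference in mortality, a hazard ratio and a p-value by Days 15, 29 and 60. Its footnotes say "HR is the hazard ratio from the Cox Proportional Hazard Model adjusted for baseline ordinal score and baseline steroid use" and "P-value is based on the Cox adjusted model". There is no interaction row and no treatment-by-CRP term.

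The SAP treats this split differently for other endpoints. The note to Table 5 reads "Add subgroup analysis for baseline CRP < 150 mg/L vs baseline CRP ≥ 150 mg/L", restricted to scores 5 or 6 and age under 85. The notes to Tables 8 and 11 say the same. Their parent formats (Tables 4, 7 and 10) have a row for the interaction p-value; the Table 4 footnote says "P-value from the interaction between the subgroup variable and treatment group is also reported".

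Mortality is an other secondary endpoint, outside the testing hierarchy (SAP Section 6.8). SAP Table 1 refers covariates and subgroups for such endpoints to the master SAP.

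**The concern.** The CRP cutoff comes from a post hoc analysis of LIVE-AIR. Protocol Section 1.1 reports that mortality did not differ significantly in the full LIVE-AIR population (p=0.241), while "in the subgroup of subjects with a CRP < 150 mg/L and age < 85 years this was statistically significant" (p=0.033, unadjusted for multiple comparisons). Protocol Section 1.1.1 concedes that the subgroup effect may be too optimistic.

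Tables 13 and 15 set up a similar contrast in BET-B: one p-value from a large group and one from a small group. A significant result in one and a non-significant result in the other says little about whether the effects differ, because the smaller group has fewer deaths and less power. At stake is whether a reader takes a mortality benefit to be limited to CRP<150 when the data do not show that.

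**Working it through.** **The plan's own figure.** Protocol Section 9.1 gives 80% and 89% power for the primary endpoint with 400 subjects, odds ratio 2.5, control rates 16% and 21%, and two-sided alpha 0.049. With 200 per arm the treated rates are 7.08% and 9.61%. Unpooled two-proportion power is 80.3% and 89.2% (pooled 79.7% and 88.7%), so the figure reproduces. No power is stated for mortality or for CRP>=150.

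**Inputs from the documents.**
- CRP<150 group: 400 (Protocol 9.1), split 1:1 (Protocol 5).
- CRP<150 share in LIVE-AIR: 78% (Protocol 1.1.1), so CRP>=150 is 400 × 0.22/0.78 = 113. At the 75% subgroup share, 400/0.75 = 533 are randomised and 133 fall outside the subgroup. These include score 7 and age 85 or over, so 133 is a ceiling.
- LIVE-AIR mortality: 13.8% placebo vs 6.5%, HR 2.2 (subgroup); 13.9% vs 9.5%, HR 1.38 (overall). These ratios exceed 1 when lenzilumab is better, and the same direction is used here.

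**Assumptions.** Placebo mortality is 10% or 13.8% below 150 and 13.8%, 20% or 30% above; the documents give no figure for CRP>=150. HR 1.8 is an intermediate value. Two-sided alpha is 0.05 for mortality, for which the plan states none. No dropout.

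**Formulas.** Treated mortality pt = 1 − (1 − pc)^(1/HR). Deaths E = (n/2)(pc + pt). Power = Φ(½ ln(HR) √E − 1.96). With independent groups and a common HR, P(significant only below 150) = power below × (1 − power above).

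**Worked case, HR 2.2, 13.8% in both groups.** pt = 1 − 0.862^(1/2.2) = 6.5%. Below 150: E = 200 × (0.138 + 0.065) = 40.7, power Φ(2.51 − 1.96) = 71%. Above 150: E = 56.5 × 0.203 = 11.5, power Φ(1.34 − 1.96) = 27%. P(only below) = 0.71 × 0.73 = 52%.

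**All cases with 113 above 150.** Triplets are for placebo mortality of 13.8 / 20 / 30% above 150.

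| HR (equal in both) | Placebo mortality <150 | Power <150 | Power >=150 | Significant only <150 | >=150 non-significant, given <150 significant |
|---|---|---|---|---|---|
| 1.38 | 10% | 16% | 9 / 11 / 14% | 14 / 14 / 13% | 91 / 89 / 86% |
| 1.38 | 13.8% | 20% | 9 / 11 / 14% | 18 / 18 / 17% | 91 / 89 / 86% |
| 1.8 | 10% | 38% | 18 / 24 / 33% | 31 / 29 / 25% | 82 / 76 / 67% |
| 1.8 | 13.8% | 49% | 18 / 24 / 33% | 40 / 37 / 33% | 82 / 76 / 67% |
| 2.2 | 10% | 57% | 27 / 36 / 51% | 42 / 36 / 28% | 73 / 64 / 49% |
| 2.2 | 13.8% | 71% | 27 / 36 / 51% | 52 / 45 / 35% | 73 / 64 / 49% |

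A log-rank simulation of the three cases in the last row gave 52, 46 and 36%. Varying the CRP>=150 group from 80 to 133 widens the overall range to 13-57%.

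**What an interaction test would do.** Under equal effects, simulation gives interaction p<0.05 in 3-5% of trials, near the nominal rate. For power, SE of the log ratio of HRs = √(4/E1 + 4/E2). Suppose HR 2.2 held only below 150, with placebo mortality 13.8% and 20%. If there is no effect above 150, E2 = 113 × 0.20 = 22.6, SE = √(4/40.7 + 4/22.6) = 0.525 and power = Φ(0.788/0.525 − 1.96) = 32%. With the smaller equal-effect count of 16.7 deaths, SE is 0.581 and power 27%. On equal-effect death counts, 80% power needs a ratio of HRs of about 4.5 (HR 1.38) to 5.1 (HR 2.2).

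**The case against.** The strongest reply is that the plan never says Tables 13 and 15 will be compared by significance. Mortality has no place in the hierarchy, each table gives hazard ratios and intervals, and Table 14 gives the full ITT result. A careful reader can compare estimates. The main CRP question concerns ventilation or death, which includes death, and there the split already has an interaction p-value. SAP Section 8.3 also says the master SAP will be followed for other secondary endpoints, so a mortality interaction may be planned there.

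Most of this stands and limits the severity. It does not remove the gap: the appendix lists Tables 13 to 15 as specific to BET-B, their format has no comparison, and no reason is given for treating mortality differently.

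A second reply is that the interaction test is too weak to help. Its power is indeed low. That argues for showing the ratio with its interval, since the interval makes the uncertainty plain and two separate p-values do not.

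A reader might also infer that LIVE-AIR mortality benefit was confined to CRP<150. The protocol does not support that: it reports the subgroup and the full population, and gives no mortality for CRP>=150.

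**Conclusion.** The point holds as a reporting gap in the BET-B SAP. With about 113 subjects against 400, an equal effect appears significant only below 150 in about 13-52% of trials. The low end is at the overall LIVE-AIR hazard ratio (13-18% at 1.38). The high end needs the subgroup hazard ratio of 2.2 and equal placebo mortality in the two groups.

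A reader might infer that an equal effect will usually look confined to CRP<150. The figures do not support that. The pattern passes one half only when the HR is about 2 or more and mortality above 150 is no higher, or little higher, than below. At HR 1.38 the commonest result is no significance in either group. The word fits most scenarios only after a significant Table 13, when Table 15 is non-significant in about 49-91% of trials, and even then not all of them.

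Nor do the documents show that the sponsor intends to conclude that benefit is limited to CRP<150, or that no mortality interaction is planned anywhere. The sizes rest on the LIVE-AIR CRP share applying here and on assumed mortality above 150. This is a cheap improvement, not a threat to the primary analysis.

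**What to change.** For time to death by Day 29 and by Day 60, fit one Cox model in subjects with scores 5 or 6 and age under 85, with treatment, CRP group (<150, >=150), their interaction, and the covariates already planned for Table 13. Report the ratio of hazard ratios with its 95% CI and the interaction p-value beside Tables 13 and 15. State that the CRP-specific mortality p-values in both tables are descriptive and will not be contrasted by significance. Dropping the p-value from Table 15 alone would deepen the asymmetry. If the master SAP already plans this comparison, a cross-reference is enough.

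The cost is one extra model at each time point, on data already collected. The drawback is low power, roughly 27-32% if HR 2.2 held only below 150. The interval will be wide, and the SAP should say that a non-significant interaction does not show equal effects.

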## APPENDIX 2. FIGURE MOCK-UPS

General Programming Notes for figures:

- Treatment group labeling will be the following will vary by stage. Abbreviations will be used if the treatment group labels need to be abbreviated to improve fit.
- Use the same color for a treatment on the different graphs (SAS standard colors):
  - Lenzilumab + RDV = Blue
  - Placebo + RDV = Red
- For severity graphs (SAS standard colors):
  - 5 = green
  - 6 = blue
  - 7 = red
  - Death = black

**Figure 2: Kaplan-Meier Plot for Time to Mechanical Ventilation or Death through Day 29 - ITT Population**

**Figure 3: Kaplan-Meier Plot for Time to Sustained Recovery through Day 60 defined by 8-point Ordinal Scale - ITT Population with Baseline Ordinal Score of 5 or 6, CRP<150 mg/L, and age<85 years**

*[Implementation note: For time to sustained recovery, create individual figures 8A through 8F for all subjects, baseline steroid use=Yes, No and baseline ordinals score=5,6]*

[figure not shown]
[figure not shown]

Figure with Similar Format:

**Figure 4: Kaplan-Meier Plot for Time to Sustained Recovery through Day 60 defined by 8-point Ordinal Scale - ITT Population**

**Figure 5: Adjusted Hazard Ratios and 95% Confidence Intervals of Time to Mechanical Ventilation or Death through Study Visit Day 29 Using a Cox Proportional Hazard Model Overall and for each Subgroup - ITT Population with Baseline Ordinal Score of 5 or 6, CRP<150 mg/L, and age<85 years**

*[Implementation note: The figure below is a shell. The final figure will include all subgroups from [Table 1](#).]*

Figures with Similar Format:

**Figure 6: Adjusted Hazard Ratios and 95% Confidence Interval of Time to Mechanical Ventilation or Death through Study Visit Day 29 Using a Cox Proportional Hazard Model Overall and for each Subgroup – ITT Population**

**Figure 7: Adjusted Hazard Ratios and 95% Confidence Interval of Time to Sustained Recovery through Study Visit Day 60 Using a Cox Proportional Hazard Model Overall and for each Subgroup – ITT Population with Baseline Ordinal Score of 5 or 6, CRP<150 mg/L, and age<85 years**

**Figure 8: Adjusted Hazard Ratios and 95% Confidence Interval of Time to Sustained Recovery through Study Visit Day 60 Using a Cox Proportional Hazard Model Overall and for each Subgroup – ITT Population**

**Figure 9: P-values from Tipping Point Analysis for the Proportion of Subjects Alive and Without Mechanical Ventilation through Day 29 — ITT Population with Baseline Ordinal Score of 5 or 6, CRP<150 mg/L, and age<85 years**

*[Implementation note: Use the ‘TippingPoint’ R package to generate this figure following the example saved here: <https://mran.microsoft.com/snapshot/2016-07-08/web/packages/TippingPoint/vignettes/TippingPoint.html>*

*R code from this package will be updated to present p-values from logistic regression. Color shading will be added to illustrate which areas of the graph show significant statistical difference. The x and y axes will be added to present proportion of events among nonresponders instead of number of events.*

*Update the x-axis label to be ‘Probability of event among nonresponders in Lenzilumab + RDV group’.*

*Update the y-axis label to be ‘Probability of event among nonresponders in Placebo + RDV group’.]*

[figure not shown]

Figure with same format:

**Figure 10: P-values from Tipping Point Analysis for the Proportion of Subjects Alive and Without Mechanical Ventilation through Day 29 — ITT Population**
